Co-Investigators	, [name] (Iron River Hospital, MI) [name] (Elkhart Hospital, IN)
Type of Study	Prospective, investigator initiated, multicenter, non-randomized single arm, open label.
Study Duration	6 Months for primary endpoint. 1 and 2 year follow-up for QOL per SOC.
Number of Patients Number of Sites	50 patients from 3 sites
Follow-Up Schedule	Following TIF procedure, patients will be expected to complete follow-up visits at the 2-Week, 3-Month, and 6-Month time points. Additional follow-up to be completed at 12 and 24 months to assess long-term symptom relief. Consideration will be given to extending follow-up with questionnaires to 3, 4 and 5 years. The study will be considered complete (with regard to the primary effectiveness endpoint) after all patients have completed the 6-Month follow-up visit.

Inclusion Criteria	
 1. Age 18-80 years 2. Dependent upon daily PPIs for > 6 months. Daily use is defined as a double dose, or full dose or half dose taken daily for more than 80% of the total number of days during the proceeding evaluation period 3. Troublesome symptoms, specifically heartburn or regurgitation, while on optimized dose of PPI's Troublesome heartburn or regurgitation symptoms are those which occur a minimum of 2 days a week and are mild to severe in severity 4. Abnormal ambulatory (Bravo) pH study after off PPI therapy for 7 days, i.e. > 5.3% of the time with pH < 4 in a 48-hour monitoring period 5. Normal or near normal esophageal motility (by Upper GI/ esophagram or manometry as required) 6. Pre-enrollment Hiatal Hernia (axial height and transverse dimension) from > 2 cm up to 4 cm inclusive. 7. Patient willing to cooperate with post-operative dietary recommendations and assessment tests at the requisite follow-up visits 8. Signed informed consent

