8.5. Esophageal Motility

- Measures LES resting pressure following standard protocol
- $> 50\%$ peristalsis with $> 30\%$ distal amplitudes
- 10 consecutive water swallows allows the assessment of propulsive motor function of the esophagus
- High-resolution motility is optional

9. Study Procedures

The schedule of observations and assessments to take place during the study follows on the next page. (**Table 4**)

Table 4. Study Events Schedule

	Initial Screening	Final Screening	Procedure	Post-Procedure/ Hospital Discharge	2-Week ±3 days	3-Month ± 15days	6-Month ± 20 days	12 and 24 Months ± 20 days
Inclusion/Exclusion Criteria	X	X						
Sign Informed Consent Form		X						
Demographics and Medical History	X							
Physical examination	X			X				
Record concomitant medications	X	X	X	X	X	X	X	
Recording of GERD Medications	X				X	X	X	X
Recording of duration of GERD Symptoms	X				X	X	X	X
Recording of type of GERD Symptoms	X				X	X	X	X
Recording of PPI Use; except for 2-week and 3-month visits, discontinue PPI usage for 7 days to evaluate study endpoints	X			X	X	X	X	X
RDQ, atypical symptom RSI, Quality of Life questionnaires GSRS, HRQL after being off PPI for at least 7 days	X						X	X
Discontinuation of anticoagulants if applicable (at least 10 days before scheduled TIF)	X							
EGD with optional biopsy		X					X	
Motility studies (High resolution optional)		X						
BRAVO pH study (at least 7 days after stopping all antisecretory compounds)		X					X	
Study Enrollment		X						
Hiatal Hernia Repair			X					
TIF 2.0 Procedure (if Hiatal Hernia successfully repaired with at least 2 cm of intra-abdominal esophagus)			X					
Adverse Event Reporting			X	X	X	X	X	

9.1. *Determination of Patient Eligibility – Screening Process*

Initial Screening -

The following pre-procedure data must be collected in order to determine patient eligibility:

- Demographics and medical history, to include age, weight, gender, and race
- Usage of GERD medication (medication, dosage, frequency and duration)
- Duration of GERD symptoms
- Type of GERD symptoms
- Duration of PPI Use
- Clinical symptom assessments (RDQ) and Quality of Life questionnaires (GSRS, HRQL, Atypical Symptom RSI)
- All general inclusion/exclusion criteria have been met

Upon completion of the Initial Screening Process, if it is determined that the patient does not have “troublesome” symptoms while on PPIs, they are **NOT eligible** for the study

Final Screening :-

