The following pre-procedure data must be collected in order to determine eligibility:

- Informed consent signing
- Physical Examination
- Days since last PPI intake (prior to BRAVO pH study)
- EGD with optional biopsy
- High resolution motility studies (optional)
- Upper GI endoscopy
- Bravo pH studies (48 hours)

Patients who have met all entry criteria are enrolled to the study.

9.2. *Prior to the Study Procedure*

- The usage of any anticoagulants will be discontinued before TIF for at least 10 days.
- 12-hours before the procedure, the patient is expected to be fasting.
- Immediately before the procedure, each patient will undergo an endoscopic examination of the stomach and esophagus.

9.3. *During the Study Procedure*

A Transoral Incisionless Fundoplication will be performed following the standard laparoscopic Hiatal Hernia Repair and closure of the diaphragmatic defect (crura closure will be made

posterior with 2-3 separate stitches). The patient will be terminated from the study if hiatal hernia cannot be repaired, with at least 2 cm intra-abdominal esophageal length.

TIF Procedure (Treatment)

The TIF procedure (treatment) will be conducted under continuous visualization following a standard TIF2.0 protocol (**Figures 8**).

[figure not shown]

Figure 8. Standard TIF2 protocol

The usage of any anticoagulants will be discontinued before HHR and TIF 2.0 for at least 10 days. Patients are expected to fast for 12 hours before the procedure. Antibiotic prophylaxis will be administered during induction of general anesthesia (oro-tracheal intubation and anti-emetic protocol; dehydrobenzoperidol, dexamethasone, Zofran, Primperan).

As stated in Section 10.2, immediately before the procedure, each patient will undergo an endoscopic examination of the stomach and esophagus. The EsophyX ZR will be inserted transorally through a bite-block into the esophagus with the patient in either in supine, or 45 degrees or left lateral position.

During a single insertion of the device, a valve similar to that created through antireflux surgery will be reconstructed by retraction of full-thickness plications and tailored placement of multiple fasteners circumferentially 1-3 cm above the Z-line. The procedure is expected to last for 30-45 minutes. The quality of the

created valve will be evaluated by an endoscopic examination immediately after the procedure. Any complications related to the procedure will be recorded.

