In the event of patient complaint of significant unmanaged GERD symptoms 14 days post procedure, the patient will be offered continued PPI therapy. (See below)

9.4. *Post-Procedure / Hospital Discharge*

Patients will be released the next day after a complete physical examination and instructed to consume a liquid diet during the first two weeks and a soft diet during the following four weeks. The liquid diet will consist of strained soups, pudding, milk, gelatin, yogurt, well-cooked and puréed vegetables, and chewable multivitamins. During weeks 3 to 6, patients will introduce a soft diet consisting of moist fish, canned fruits, bananas, berries, soft eggs, cooked vegetables, mashed potatoes, pasta, moist rice, and cereals (softened in milk). After the six-week healing time, patients can then incorporate fresh vegetables, meats, bread, citrus and alcohol back into their diet.

The usage of PPIs will be continued for 14 days following the procedure to allow healing of the gastric mucosa around the fasteners and to reduce patients' post procedure anxiety. In the event of the recurrence of troublesome symptoms, patients will be encouraged to contact the study coordinator. The nature, intensity and frequency of these symptoms will be assessed during in-office visits.

The designated staff at the clinical site will review the study requirements with the patient to maximize compliance with the follow-up schedule and the required medication regimen. Patients will be instructed to return for follow-up assessments according to the study event schedule in Section 8. A date for the follow-up visit (office or phone as appropriate) should be established between the patient and Investigator, and if possible the visits scheduled at the time of hospital discharge.

9.5. *Follow-up*

All enrolled patients will be evaluated at 2-weeks, 3-, 6-, and 12-Months and 24 months post TIF- procedure.

The study will be considered complete (with regard to the primary endpoint) after all patients have completed the 6-Month follow-up period.

Consultations may become necessary if major reflux symptoms emerge. Before each follow up time point the patient will be contacted by telephone in order to enhance clinical assessments and data compliance. Refer to the Schedule of Events (**Table 4**) for a comprehensive outline of protocol requirements.

10. Statistical Considerations

10.1. *Analysis Populations and Missing Data Handling*

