Effectiveness Population - Per the Intent-to-Treat principle, all enrolled patients who receive the protocol TIF 2.0 procedure will be included in the effectiveness analysis.

Safety Population - Safety analysis will include all enrolled patients who receive any portion of the protocol required Hiatal Hernia Repair or TIF 2.0 procedures.

Missing data: All analyses will be based on available data. Missing data will not be imputed by methods.

10.2. *Statistical Analysis Plan*

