10.2.2 Effectiveness Analysis

The primary analysis timepoint for effectiveness is 6 months post TIF procedure. Descriptive summaries as described in 10.2.1 General Methodology will be provided for the primary effectiveness endpoint of proportion of patients with normalized esophageal acid exposure, and secondary endpoints of proportion of patients free of “troublesome” symptoms and proportion of patients with a clinically significant reduction in PPI consumption from their pre-TIF screening consumption.

At each assessment time point, RDQ, atypical symptom RSI, Quality of Life questionnaires GSRS, HRQL will summarized as continuous measures. At 6 months, changes from baseline will be similarly summarized for each of these instruments. As defined in Section 8.1, portions of patients with clinically significant improvements will also be reported with 95% confidence intervals for GERD-HRQL, GERD-GSRS, RSI, and RDQ.

In addition, for the primary endpoint, proportion of patients with normalized esophageal acid exposure, 44% was observed in the EGS RESPECT study. Non-inferiority testing will be conducted for the same proportion observed in the HEURISTIC study vs. the RESPECT result. The hypotheses are as follows.

H_0 : HEURISTIC 6-month normalization rate $\leq 44\% - 20\% = 24\%$

H_A : HEURISTIC 6-month normalization rate $> 44\% - 20\% = 24\%$

The HEURISTIC normalization rate will be considered non-inferior to the 44% RESPECT rate if H_0 can be rejected at a 1-sided $p < 0.05$ level by exact binomial

probability calculation. To achieve this goal in 50 evaluable patients, the observed 6-month normalization rate in HEURISTIC must be 18/50 (36%) or higher.

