10.2.3 Safety Analysis

Treatment emergent adverse events, i.e. adverse events occurring during or after the first protocol procedure (i.e. hiatal hernia reduction), will be summarized. The proportion of patients with medically significant adverse events will be compared to the same proportions observed in the RESPECT study.

In addition, the number and proportion of subjects reporting any given adverse event, including any clinically significant hiatal hernia repair complications and new onset symptoms (dysphagia, gas bloat) should they occur, will be tabulated. Separate tables will be constructed for (a) all reported treatment emergent adverse events, (b) protocol procedures (hiatal hernia reduction, TIF) related adverse events, and (c) serious adverse events.

10.1. *Sample Size and Power Estimation*

For the primary endpoint, proportion of patients with normalized esophageal acid exposure at 6 months post TIF procedure, 44% was observed in the EGS RESPECT study. It is assumed that the true underlying rate for HEURISTIC treatment would be the same, i.e. 44%. In order to reject an inferior normalization rate of 24% at a 1-sided $p < 0.05$ level, the observed 6-month normalization rate in HEURISTIC must be 18/50 (36%) or higher. With 50 evaluable subjects, the chance (power) for successfully reaching this goal is 0.90.

11. Clinical Effectiveness Endpoints and Evaluation Criteria

11.1. *Clinical effectiveness*

Primary effectiveness endpoint and evaluation criterion

The primary efficacy endpoint is normalization in esophageal acid exposure at 6 months post TIF procedure. Normalization in esophageal acid exposure is defined as $\leq 5.3\%$ of time with $\text{pH} < 4$ in a 48-hour monitoring period.

Secondary effectiveness measures and evaluation criteria

Secondary effectiveness measures include free of “troublesome” heartburn and/or regurgitation symptoms and a clinically significant reduction in PPI use.

Per Montreal Consensus definition, troublesome symptoms are mild to severe symptoms which occur a minimum of 2 days a week.

A clinically significant PPI consumption reduction is defined as from daily use to occasional use or none at all. Daily use is defined as a double dose, or full dose or half dose taken daily for more than 80 % of the total number of days during the proceeding follow-up period.

Table 5. Study Effectiveness Endpoints and Success Criteria

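### Section 10.1 includes all TIF 2.0 recipients by intent-to-treat but analyses available data only, so treated patients with no 6-month pH result drop out of the primary test and no sensitivity analysis shows whether this matters

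*Combined protocol and SAP*

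**What the plan says.** Section 10.1 (Analysis Populations and Missing Data Handling) defines the effectiveness set: "Per the Intent-to-Treat principle, all enrolled patients who receive the protocol TIF 2.0 procedure will be included in the effectiveness analysis". The same section then sets the missing-data rule: "Missing data: All analyses will be based on available data. Missing data will not be imputed by methods".

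Section 10.2.2 tests the 6-month normalization rate against 24% (44% from RESPECT less a 20-point margin) by exact binomial calculation at one-sided 0.05, and adds: "To achieve this goal in 50 evaluable patients, the observed 6-month normalization rate in HEURISTIC must be 18/50 (36%) or higher". The sample size section states: "With 50 evaluable subjects, the chance (power) for successfully reaching this goal is 0.90". The synopsis plans "50 patients from 3 sites", which is the same number.

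The word evaluable is not defined. No section assigns an outcome to a treated patient without a 6-month pH result, and none plans a missing-data sensitivity analysis.

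Three provisions bear on who might lack a result:
- Section 7.2 ends follow-up for withdrawn patients.
- Section 9.3 covers failed repairs: "The patient will be terminated from the study if hiatal hernia cannot be repaired, with at least 2 cm intra-abdominal esophageal length".
- Section 9.3 also says: "In the event of patient complaint of significant unmanaged GERD symptoms 14 days post procedure, the patient will be offered continued PPI therapy".

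Three others limit loss:
- Section 9.5 plans a telephone call before each visit.
- Section 13.3 keeps all enrolled patients in follow-up unless they withdraw consent.
- Table 4 instructs sites to "discontinue PPI usage for 7 days to evaluate study endpoints", exempting only the 2-week and 3-month visits.

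**The concern.** For a binary endpoint, a treated patient can stay in the denominator only if some outcome is assigned. The available-data rule assigns none, so the intent-to-treat label and the analysis rule give different denominators whenever a pH result is absent.

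This matters here because the primary test is the only one with a stated null hypothesis and level, and it compares a single arm with a fixed number. No concurrent control group would share the same losses. If patients who did not normalize are less likely to return for the pH study, the observed rate is biased upward and the test can declare non-inferiority too often. If normalizers are the ones who skip it, the bias runs the other way. The plan includes nothing to show how far the conclusion depends on the missing patients.

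**Working it through.** **Inputs from the documents.** Null rate 0.24, assumed true rate 0.44, one-sided level 0.05, exact binomial test (Section 10.2.2 and the sample size section); 50 patients (synopsis).

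**Assumptions.** 50 patients treated; the amount and pattern of missing pH results, since the documents give neither.

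**Step 1: reproduce the plan.**
- P(X ≥ 18 | 50, 0.24) = 0.0384 and P(X ≥ 17 | 50, 0.24) = 0.0718, so 18/50 is the correct threshold.
- P(X ≥ 18 | 50, 0.44) = 0.901, which agrees with the stated 0.90.
- The exact level is 3.84%, so there is some slack below 5%.

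**Step 2: level of the available-data test.** Let m be the expected number missing and L = m/50. Each normalizer is missing with probability s and each failure with probability f = k × s.
- s = L / (0.24 + 0.76k). If only failures are missing, s = 0 and f = L/0.76.
- The number observed, n, is Binomial(50, 1 − L).
- The normalization rate among those observed is q = 0.24(1 − s)/(1 − L).
- c(n) is the smallest count with one-sided p < 0.05 against 0.24: 18 for n = 48 to 50, 17 for 45 to 47, 16 for 42 to 44, 15 for 40 and 41.
- Level = Σ P(n) × P(X ≥ c(n) | n, q).

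Example with k = 2 and m = 5: s = 0.10/1.76 = 0.0568, f = 0.1136, q = 0.24 × 0.9432/0.90 = 0.2515, level 5.3%. With only failures missing and m = 5: f = 0.10/0.76 = 0.1316, q = 0.24/0.90 = 0.2667, level 8.4%.

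False-success probability at a true rate of 24%:

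| Who is missing | m = 3 | m = 5 | m = 6 | m = 10 |
|---|---|---|---|---|
| Normalizers twice as likely | 2.33% | 1.87% | 1.65% | 0.83% |
| Unrelated to outcome | 3.36% | 3.53% | 3.60% | 3.61% |
| Failures 1.5 times as likely | 3.92% | 4.57% | 4.91% | 6.13% |
| Failures twice as likely | 4.27% | 5.26% | 5.80% | 8.02% |
| Only failures (bound) | 5.74% | 8.38% | 10.00% | 18.11% |

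For unrelated loss, the range over m = 1 to 10 is 3.3% to 3.7%. The 2:1 curve crosses 5% between 4.5 and 4.6 expected missing, and the bound crosses at 2.3.

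**Step 3: can a conclusion reverse?** 17/47 gives p = 0.042 and passes. If all three missing patients failed, 17/50 gives p = 0.072 and does not. Likewise 16/44 gives p = 0.045 and 16/50 gives p = 0.125. In the first case one normalizer among the three would restore 18/50. That has probability 1 − 0.76³ = 0.56 at a 24% rate, or 1 − 0.64³ = 0.74 at 36%.

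**Step 4: count missing as not normalized, all 50 treated in the denominator.** The counted normalizers can never exceed the true normalizers, so the level is at most P(X ≥ 18 | 50, 0.24) = 3.8% under any missing pattern. Power at a true 44% with unrelated loss L is P(X ≥ 18 | 50, 0.44(1 − L)):

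| Loss | Rate used | Missing = not normalized | Available-case |
|---|---|---|---|
| 0 | 0.440 | 0.901 | 0.901 |
| 5% | 0.418 | 0.835 | 0.872 |
| 10% | 0.396 | 0.745 | 0.861 |

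**The case against.** The inflation is hypothetical. The documents give no loss rate, and the exact test has slack: with failures 1.5 times as likely to be missing, the level is still below 5% at 6 expected missing. The largest figures need every missing patient to be a failure, as do the reversals in Step 3. All of this stands, and those figures are given as bounds or examples.

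A reader might infer that the offer of continued PPI makes failures the likely absentees. The documents do not establish that. The offer is tied to 14 days after the procedure, and Table 4 still requires the washout for the 6-month endpoint. Every enrolled patient has already completed a 7-day washout with a Bravo study and agreed to the follow-up tests (inclusion criteria 4 and 7). Failure-related loss is plausible, but so is a well patient declining a repeat test.

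A reader might also infer that a pH study done without the full washout is excluded. No text says so; the available-data rule removes only patients with no result.

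The two sentences of Section 10.1 can be read together, one defining the set and the other the handling of gaps, with evaluable meaning that a result exists. On that reading the label is loose rather than contradictory, but the denominator still shrinks and its effect is still not examined.

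Finally, counting missing as failure costs power, and how RESPECT handled missing data for its 44% is not given. That is a fair reason not to insist on it as the sole primary analysis.

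**Conclusion.** The gap in the text is certain: an intent-to-treat label, an available-data rule, an undefined evaluable set and no sensitivity analysis. The effect on the test is conditional on the assumptions in Step 2. With 50 treated, unrelated loss leaves the level below 5% and only costs power. Breaching 5% needs about 4.6 expected missing if failures are twice as likely to be lost, or between 6 and 10 at 1.5 times. Even in the bound where only failures are lost, it needs 2.3.

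The stronger reading, that the plan as written inflates the false-success rate, is not supported, because the documents give neither the amount nor the direction of loss. Nor is the 0.90 power wrong: it is stated for 50 evaluable subjects and reproduces. What is missing is any allowance between 50 planned and 50 evaluable, including for patients terminated before TIF. This should be fixed before results are seen, because a few missing patients could decide the conclusion.

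**What to change.** In Sections 10.1 and 10.2.2:
- Define evaluable, and reconcile the intent-to-treat sentence with the available-data sentence so that the primary denominator is explicit.
- Alongside the available-case test, pre-specify an analysis with all TIF 2.0 recipients in the denominator and a missing 6-month pH result counted as not normalized.
- Pre-specify a tipping-point analysis giving the number of missing patients who would have to be normalizers for the conclusion to hold. It cannot reveal the true missing pattern; it shows how much the conclusion depends on it.
- Call the non-inferiority conclusion robust only if it survives these analyses. Making the all-treated analysis primary is an option that fits the intent-to-treat label.

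In the sample size section, state that the 0.90 power applies only if all 50 planned patients are evaluable.

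The cost is SAP wording and minor programming, with no new data and no change in the number of patients. The downside is that the all-treated analysis is conservative: power is about 0.84 at 5% and 0.75 at 10% unrelated loss, against 0.87 and 0.86 available-case. It may also be stricter than whatever rule lies behind the 44% from RESPECT, which is why both results should be reported.

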10.2.1 General Methodology

Patient demographics and key baseline and disease characteristics at screening will be summarized by descriptive statistics. Mean, standard deviation, median, minimum and maximum will be reported for continuous variables. Frequency counts and proportions will be presented for categorical variables. Effectiveness and Safety endpoints will be similarly summarized with 95% confidence intervals for means and proportions of interest.

